### ***Risk assessment for study holding rules***

Figure 1 illustrates that, with 27 participants in the co-administration group in the pre-specified scheduled SRT review:

- Holding rule 1a has more than 76% chance of not being met for vaccination with a true incidence rate of 1% and has more than 94% chance of being met for vaccination with a true incidence rate above 10%.
- Holding rule 1d has more than 61% chance of not being met for vaccination with a true incidence rate of 5% and has more than 93% chance of being met for vaccination with a true incidence rate above 15%.
- Each holding rule 1b, 1c and 2b has more than 48% chance of not being met for vaccination with a true incidence rate below 10% and more than 79% chance of being met for vaccination with a true incidence rate above 15%.
- Holding rule 2a has more than 79% chance of not being met for vaccination with a true incidence rate below 15% and more than 70% chance of being met for vaccination with a true incidence rate above 25%.

**Figure 2 Evaluations Based on 27 Participants in the Co-administration Group. Risk Assessment Curve Based on the Proposed Safety Holding Rules**

#### 4.6 Participant Input into Design

Not applicable for this study.

## 5.0 STUDY POPULATION

Prospective approval of protocol deviations to recruitment and enrollment criteria, also known as protocol waivers or exemptions, is not permitted.

### 5.1 Inclusion Criteria

Participants are eligible to be included in the study only if all of the following criteria apply:

All participants must satisfy ALL the following criteria at study entry:

- A male or female participant  $\geq 50$  YOA at the time of the first study intervention administration.
  - Female participants of non-childbearing potential may be enrolled in the study. Non childbearing potential is defined as hysterectomy, bilateral oophorectomy, bilateral salpingectomy or post-menopause. Refer to [Section 10.4.1](#) for definitions of women not considered as women of childbearing potential, and menopause.
  - Female participants of childbearing potential may be enrolled in the study, if the participant:
    - has practiced adequate contraception from 1 month prior to study intervention administration.
    - has a negative pregnancy test on the day of and prior to study intervention administration.
    - has agreed to continue effective contraception until the end of the study.
    - Refer to [Section 10.4](#) for definitions of woman of childbearing potential and adequate contraception.
  - Participants who, in the opinion of the investigator, can and will comply with the requirements of the protocol (e.g., completion of the electronic diary [eDiary], return for follow-up visits, ability to access and utilize a phone or other electronic communications).  
*Note: In case of physical incapacity that would preclude the self-completion of the eDiary, either site staff can assist the participant (for activities performed during site visits) or the participant may assign a caregiver\* to assist him/her with this activity (for activities performed at home). However, at no time will the site staff or caregiver\* evaluate the participant's health status while answering eDiaries or make decisions on behalf of the participant.*
- \*A 'caregiver' is a person who has a continuous caring role for a participant or may be a person having substantial periods of contact with a participant and/or is engaged in his/her daily health care (e.g., a relative of the participant including family members or friends).
- Written or witnessed informed consent obtained from the participant prior to any study specific procedure being performed.

- Participants living in the general community or in an assisted-living facility that provides minimal assistance, such that the participant is primarily responsible for self-care and activities of daily living.
- Participants who are medically stable in the opinion of the investigator at the time of first study intervention administration. Participants with chronic stable medical conditions with or without specific treatment, such as diabetes mellitus, hypertension, or cardiac disease, are allowed to participate in this study if considered by the investigator as medically stable.

## 5.2 Exclusion Criteria

The following criteria should be checked at the time of study entry. The potential participant MUST NOT be included in the study if ANY exclusion criterion applies:

### 5.2.1 Medical conditions

- Pregnant or lactating female.
- Female planning to become pregnant or planning to discontinue contraceptive precautions.
- Any confirmed or suspected autoimmune disorders, immunosuppressive or immunodeficient condition resulting from disease (e.g., current malignancy, human immunodeficiency virus) or immunosuppressive/cytotoxic therapy (e.g., medication used during cancer chemotherapy, organ transplantation, or to treat autoimmune disorders), based on medical history and physical examination (no laboratory testing required).
- History of any reaction or hypersensitivity (e.g., anaphylaxis) likely to be exacerbated by any component of the study interventions, in particular any history of severe allergic reaction to any vaccine component.
- History of Guillain-Barré syndrome.
- Any history of dementia or any medical condition that moderately or severely impairs cognition.

*Note: If deemed necessary for clinical evaluation, the investigator can use tools such as Mini-Mental State Examination (MMSE), Mini-Cog or Montreal Cognitive Assessment (MoCA) to determine cognition levels of the participant.*

- Recurrent or uncontrolled neurological disorders or seizures. Participants with medically-controlled chronic neurological diseases can be enrolled in the study as per investigator assessment, provided that their condition will allow them to comply with the requirements of the protocol (e.g., completion of the eDiary, attend regular phone calls/study site visits).
- Significant underlying illness that in the opinion of the investigator would be expected to prevent completion of the study (e.g., life-threatening disease likely to limit survival up to study end).

- Any medical condition that in the judgment of the investigator would make intramuscular injection unsafe.
- Clinically suspected or polymerase chain reaction (PCR)-confirmed ongoing episode of herpes zoster.

### 5.2.2 Prior and Concomitant Therapy

- History of previous vaccination with any licensed or investigational recombinant adjuvanted zoster vaccine (HZ/su vaccine; *Shingrix*) before the study start or planned receipt through study participation.
- History of previous vaccination with any licensed or investigational live herpes zoster vaccine (*Zostavax*) in the last 2 years from enrollment, or planned receipt through study participation.
- Previous vaccination with licensed or investigational RSV vaccine.
- Use of any investigational or non-registered product (drug, vaccine or medical device) other than the study interventions during the period beginning 30 days before the first dose of study interventions, or their planned use during the study period.
- Planned or actual administration of a vaccine not foreseen by the study protocol in the period starting 30 days before the first study intervention administration and ending 30 days after the last study intervention administration.
  - In the case of COVID-19 and inactivated/subunit/split influenza vaccines, this time window can be decreased to 14 days before and after each study intervention administration provided COVID-19 vaccine use is in line with local governmental recommendations.

*Note: In case an emergency mass vaccination for an unforeseen public health threat (e.g., a pandemic) is recommended and/or organized by the public health authorities outside the routine immunization program, the time period described above can be reduced if necessary for that vaccine, provided it is used according to the local governmental recommendations and that the Sponsor is notified accordingly.*

- Planned or actual administration of adjuvanted quadrivalent influenza vaccine influenza vaccine not foreseen by the study protocol in the period starting 30 days before the first study intervention administration and ending 30 days after the last study intervention administration.
- Administration of long-acting immune-modifying drugs during the period starting 180 days before the administration of first dose of study interventions or planned administration at any time during the study period (e.g., infliximab).
- Administration of immunoglobulins and/or any blood products or plasma derivatives during the period starting 90 days before the administration of first dose of study interventions or planned administration during the study period.

- Chronic administration (defined as more than 14 consecutive days in total) of immunosuppressants or other immune-modifying drugs during the period starting 90 days prior to the first study intervention dose or planned administration during the study period. For corticosteroids, this will mean prednisone  $\geq 20$  mg/day, or equivalent. Inhaled, topical or intra-articular steroids are allowed.

#### **5.2.3 Prior/Concurrent clinical study experience**

- Concurrently participating in another clinical study, at any time during the study period, in which the participant has been or will be exposed to an investigational or a non-investigational vaccine/product (IMP) (drug or invasive medical device).

*Note: European Economic Community (EEC) directive 93/42/EEC defines an invasive medical device as 'A device which, in whole or in part, penetrates inside the body, either through a body orifice or through the surface of the body'.*

#### **5.2.4 Other exclusions**

- History of chronic alcohol consumption and/or drug abuse as deemed by the investigator to render the potential participant unable/unlikely to provide accurate safety reports or comply with study procedures.
- Bedridden participants.
- Planned move during the study conduct that prohibits participation until study end.
- Participation of any study personnel or their immediate dependents, family, or household members.

### **5.3 Lifestyle Considerations**

#### ***Meals and Dietary Restrictions***

No meal or dietary restrictions are required for study participation. No lifestyle restrictions are applicable for this study.

### **5.4 Caregiver Support**

Study participants may decide to assign a caregiver to help them fulfill the study procedures. Please refer to the [Glossary of Terms](#) for the definition of a caregiver.

A caregiver can be appointed by the participant at any time during the study, when the participant feels it is necessary. Each caregiver should receive the caregiver information letter before providing support to the study participant. Ideally, a single caregiver should be appointed by the participant but, in some situations, it may happen that several caregivers will support a study participant throughout the conduct of the study. This should be recorded in the source documents. However, every effort should be done to ensure that only one caregiver enters the data into the eDiary to allow for timely completion.

Caregivers may help the study participants with performing some practical study procedures such as receiving or making phone calls to site staff, planning study visits, transcribing responses to diaries, transportation to and from the study site etc. However, at no time, the caregiver should evaluate the participant's health status while answering diaries or make decisions on behalf of the participant. At the first study visit (Visit 1 [Day 1]) the site staff should inform the participant of the possibility to appoint a caregiver. Then at subsequent study visit(s), the site staff should check again with the participant if he/she wishes to appoint a caregiver or if there were or will be changes of caregiver.

## 5.5 Screen Failures

A screen failure occurs when a participant who has consented to participate in the clinical study is not subsequently randomized to study intervention/entered in the study.

Limited data for screening failures (including reason for screening failure and any serious adverse events (SAEs) related to study participation, or to a concurrent GSK medication/vaccine from the time of consent obtained) will be collected and reported in the electronic case report form (eCRF).

Individuals who do not meet the criteria for participation in this study (screen failure) but at some point, in the future are expected to meet the eligibility criteria may be rescreened. Individuals who are rescreened will be assigned a new participant number and will undergo the informed consent process, and then restart a new screening phase.

## 5.6 Criteria for Temporarily Delaying

Study intervention administration may be postponed within the permitted time interval as deemed appropriate by the investigator until transient conditions cited below are resolved and prior to the EoS enrollment period:

- Acute disease and/or fever at the time of study intervention administration. Refer to [Section 1.3](#) (Schedule of Activities [SoA]) for definition of fever and location for measuring body temperature in this study.
- Participants with a minor illness (such as mild diarrhea) without fever may be dosed at the discretion of the investigator.
- Participants with symptoms suggestive of active Coronavirus Disease 2019 (COVID-19) infection (e.g., fever, cough, etc.). The return of the participant to the site will follow the specific guidance from local public health and other competent authorities (e.g., free of symptoms, COVID-19 negative testing, etc.).
- Participants with known contact with COVID-19 positive individual may be vaccinated at least 14 days after the exposure, provided that the participant remains symptom-free, and at the discretion of the investigator.

- In case of administration of inactivated, subunit or split influenza vaccines or COVID-19 vaccines (fully licensed or with Emergency Use Authorization [EUA]): postponement of study intervention administration within given protocol timelines and prior to the end of the study enrollment period, to allow respect of at least 14 days interval between abovementioned influenza/COVID-19 vaccination and study intervention administration.
- Use of antipyretics and/or analgesics and/or antibiotics within 3 days prior to study intervention administration.
- Other issues (e.g., technical or administrative) preventing dose administration on day of visit.

In case of delayed enrollment, all visit activities will be repeated when the participant is able to return for the visit.

For Visit 1, if the planned study intervention administration is delayed, blood sampling does not need to be repeated if it was obtained during enrollment visit. The following procedures must be repeated prior to the delayed study intervention administration:

- Urine pregnancy test
- Body temperature
- Re-check contraindications, warnings, and precautions to study intervention
- Re-check inclusion/exclusion criteria

Visit window for Visit 2 starts from day of first study intervention administration.

For delay in the study intervention administration during Visit 2 (control group), and Visit 3 (co-administration and control groups) the following procedures must be repeated:

- Urine pregnancy test
- Body temperature
- Re-check contraindications, warnings, precautions to study intervention
- Re-check inclusion/exclusion criteria

## 6.0 STUDY INTERVENTION(S) AND CONCOMITANT THERAPY

Study intervention is defined as any investigational intervention(s), marketed product(s), placebo, or medical device(s) intended to be administered to a study participant according to the study protocol.

### 6.1 Study Intervention(s) Administered

**Table 8 Study Intervention(s) Administered**

Study Treatment Name:	RSVPreF3 OA Investigational Vaccine		Shingrix	
Vaccines/ product formulation	RSVPreF3 (120 µg)	AS01 E : QS-21* (25 µg), MPL (25 µg), liposomes; Water for injections	VZV gE (50 µg)	AS01 B : QS-21* (50 µg), MPL (50 µg), liposomes; Water for injections
Presentation	Vial; powder for suspension for injection	Vial; suspension for injection	Vial; powder for suspension for injection	Vial; suspension for injection
Route of Administration	Intramuscular use		Intramuscular use	
Product category	Biologic		Biologic	
Type	Study		Study	
Administration site				
Location	Deltoid		Deltoid	
Laterality	Co-ad group: Dominant Control group: Non-dominant		Co-ad group: Non-dominant Control group: Non-dominant	
Number of doses to be administered	1		2	
Dose Volume**	0.5 mL		0.5 mL	
Packaging, labeling***	Refer to Pharmacy Manual for details		Refer to Pharmacy Manual for details	
Manufacturer	GSK		GSK	

Abbreviations: AS01E/AS01B=adjuvant system 01; MPL=monophosphoryl lipid A; QS-21=Quillaja saponaria Molina, fraction 21; RSV=respiratory syncytial virus.

\*Licensed by GSK from Antigenics Inc, a wholly owned subsidiary of Agenus Inc., a Delaware, USA corporation.

\*\*Refer to the Pharmacy Manual for the volume after reconstitution.

\*\*\* Labeling is compliant with the requirements of applicable regulatory agencies.

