## 4.0 STUDY DESIGN

### 4.1 Overall Design

The study design diagram is provided in [Figure 1](#).

**Experimental design:** Phase III, open-label, randomized, controlled, multi-country study with 2 parallel groups.

**Study groups and Randomization:** Approximately 530 eligible participants will be randomly (1:1) assigned to 2 study groups (approximately 265 participants each) using a centralized randomization system on internet at Visit 1 (Day 1). The randomization algorithm will use a minimization procedure accounting for age (50 to 59, 60 to 69, or  $\geq$ 70 years) and center. Minimization factors will have equal weight in the minimization algorithm.

- Enrollment rules are described in [Section 4.1.2](#).

**Duration of study:** The total duration of the study, per participant, will be approximately 8 months.

- **Co-administration (Co-ad) group:** Study interventions will be administered on Visit 1 (Day 1) in which participants will receive both HZ/su vaccine and RSVPreF3 OA investigational vaccine; and on Visit 3 (Day 61) in which the second dose of HZ/su vaccine will be administered. A total of four site visits (Visit 1 [Day 1], Visit 2 [Day 31], Visit 3 [Day 61] and Visit 4 [Day 91]) and a remote contact 6 months post-last vaccination are needed.
- **Control group:** Study interventions will be administered on Visit 1 (Day 1) in which participants will receive HZ/su vaccine; Visit 2 (Day 31) in which participants will receive RSVPreF3 OA investigational vaccine; and Visit 3 (Day 61) in which participants will receive the second dose of HZ/su vaccine. A total of four site visits (Visit 1 [Day 1], Visit 2 [Day 31], Visit 3 [Day 61] and Visit 4 [Day 91]) and a remote contact 6 months post-last vaccination are needed.

The description of the vaccine(s)/product is presented in [Table 8](#).

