### **6.3.5 Blinding and Unblinding**

This is an open-label study. The participant and principal investigator (PI) will not be blind to the intervention administered.

The laboratory in charge of sample testing will be blinded to the study intervention assignment. Codes will be used to link the participant and study to each sample to be tested in the laboratory. There will be no link between the study intervention and the identity of the participant.

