### 10.3.5.2 Assessment of Intensity and Causality

Assessment of Intensity		
Table 23 Intensity Scales for Solicited Events		
Event	Intensity grade	Parameter
Pain at administration site	0	None
	1	Mild: Any pain neither interfering with nor preventing normal everyday activities.
	2	Moderate: Painful when limb is moved and interferes with everyday activities.
	3	Severe: Significant pain at rest. Prevents normal everyday activities.
Erythema at administration site		Greatest surface diameter in mm
Swelling at administration site		Greatest surface diameter in mm
Temperature*		Temperature in °C or °F.
Headache	0	None
	1	Mild: Headache that is easily tolerated
	2	Moderate: Headache that interferes with normal activity
	3	Severe: Headache that prevents normal activity
Fatigue	0	None
	1	Mild: Fatigue that is easily tolerated
	2	Moderate: Fatigue that interferes with normal activity
	3	Severe: Fatigue that prevents normal activity
Myalgia	0	None
	1	Mild: Myalgia that is easily tolerated
	2	Moderate: Myalgia that interferes with normal activity
	3	Severe: Myalgia that prevents normal activity
Arthralgia	0	None
	1	Mild: Arthralgia that is easily tolerated
	2	Moderate: Arthralgia that interferes with normal activity
	3	Severe: Arthralgia that prevents normal activity
Shivering/Chills	0	None
	1	Mild: Shivering that is easily tolerated
	2	Moderate: Shivering that interferes with normal

		activity
	3	Severe: Shivering that prevents normal activity
Gastrointestinal symptoms	0	None
	1	Mild: Gastrointestinal symptom that is easily tolerated
	2	Moderate: Gastrointestinal symptom that interferes with normal activity
	3	Severe: Gastrointestinal symptom that prevents normal activity

\*Refer to the SoA ([Section 1.3](#)) for the definition of fever and the location for temperature measurement.

The maximum intensity of injection administration site erythema/swelling and fever will be scored by investigator as follows:

	Erythema/swelling	Fever
0:	≤20 mm	<38.0 °C <100.4 °F
1:	> 20 - ≤50 mm	≥38.0 °C (100.4 °F) - ≤38.5 °C (101.3 °F)
2:	> 50 - ≤100 mm	>38.5 °C (101.3 °F) - ≤39.0 °C (102.2 °F)
3:	>100 mm	>39.0 °C (102.2 °F)

The intensity of an AE is an estimate of the relative severity of the event made by the investigator based on his or her clinical experience and familiarity with the literature. The following definitions are to be used to rate the severity of an AE:

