Secondary	RSVPreF3 OA (one dose) and HZ/su (two doses) co-administered (Co-Ad) or received separately (Control)	Adults aged $\geq 50$ YOA	MGIs for RSV-B neutralizing titers	
1. Permanently discontinued from study due to any reasons prior to 30 days after vaccine administration (Visit 4 for Co-Ad group and Visit 3 for Control group)
 
2. Study intervention not administered per protocol
 
3. Prohibited medication or intercurrent medical condition (Visit 4 for Co-Ad group and Visit 3 for Control group)
 
4. RSVPreF3 OA investigational vaccine or blood sample for RSV neutralizing titers (for baseline or testing) taken out of window
 
5. No pre / post-vaccine immunogenicity results for
	
1. Missing data won't be imputed. Summaries will present the actual data.
 
2. Participant excluded from the immunogenicity analysis.
 
3. Participant excluded from the immunogenicity analysis.
 
4. Participant excluded from the immunogenicity analysis.
 
5. Participant excluded from the immunogenicity analysis.
	MGIs of the within participants ratios for the RSV-B neutralizing titers at 1-month after the RSVPreF3 OA dose (Visit 2 for Co-Ad group; Visit 3 for the Control group) over pre-vaccination.
-----------	---	---------------------------	------------------------------------	--	--	---

				RSV-B neutralizing titers available		
Secondary	RSVPreF3 OA (one dose) and HZ/su (two doses) co-administered (Co-Ad) or received separately (Control)	Adults aged $\geq 50$ YOA	Solicited administration site events within 7 days after each vaccine administration	1. eDiary not completed on each day	1. Missing data won't be imputed. Compliance to eDiary will be captured	Percentage and exact 95% CIs of participants with solicited administration site events within 7 days after each vaccine administration (Days 1-7 after each vaccine, HZ/su and RSVPreF3 OA) [i.e., date of RSVPreF3 OA vaccine administration for Control group becomes Day 1 for recording events within 7 days]).

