## 16.1. Adverse Events

Adverse Events (AEs) will be coded using MedDRA central coding dictionary, version 25.1 or higher. Adverse events will be described using frequency and percentage.

Adverse Events will be grouped by SOC, HLT and PT and summarized by study intervention group at time of onset of the AE. The summary tables will present the number and percentage of total participants and number of events, by SOC and by PT for each study intervention.

For the summaries of AEs, participants who experience the same AE (in terms of the MedDRA SOC, HLT and PT) more than once will only be counted once for that event in the number of participants but all occurrences of the same event will be counted in the number of events. Also, in the case of co-administered study interventions, an administration site event recorded for a participant following multiple study interventions will be counted as only one occurrence.

Causality, as indicated by the Investigator is classed as “related” and “not related” to RSVPreF3 vaccine and to HZ/su vaccine. A “related” AE is an AE with reasonable probability of being related to the medicinal products in the opinion of the investigator. If a participant reports multiple events with different severity within that SOC / PT, then the subject will be counted only once at the worst-case relationship to study intervention for the number of subjects.

[figure not shown]
See [APPENDIX 2](#) for handling of partial dates for AEs.

Summaries of events causally related to study intervention will be reported separately for each study intervention (RSVPreF3 OA and HZ/su).

Some of the key safety analysis will be generated by age group at first vaccination: 50-59 YOA, 60-69 YOA, and  $\geq 70$  YOA.

For clinicaltrials.gov and EudraCT posting purposes, percentage of participants of combined solicited and unsolicited non-serious adverse events during the 30-day follow-up period (i.e., the day of vaccination and 29 subsequent days) will be produced by System Organ Class and preferred terms and according to occurrence of each event.

CCI

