**Table K: Solicited events lower level term codes and decodes**

Solicited event	Lower level term code	Corresponding Lower level term decode
Pain	10022086	Injection site pain
Erythema	10022061	Injection site erythema
Swelling	10053425	Injection site swelling
Fever	10016558	Fever
Headache	10019211	Headache
Fatigue	10016256	Fatigue
Myalgia	10028411	Myalgia
Arthralgia	10003239	Arthralgia
Shivering/Chills	10008531	Chills
Diarrhoea	10012735	Diarrhoea
Abdominal pain	10000081	Abdominal pain
Nausea	10028813	Nausea
Vomiting	10047700	Vomiting

Solicited events will be summarized and listed as:

- The number and percentage of participants with at least one administration site event (solicited only), with at least one systemic event (solicited only) and with any solicited event during 4-day follow-up and 7-day follow-

CCI

up period after vaccination, and also events ongoing at the end of the 7 day follow up period, will be tabulated with exact 95% CI by visit. These summaries will be repeated by age group.

- The number and percentage of participants, with exact 95% CIs, reporting each solicited events (administration site and/or systemic) will be summarized separately for all grades, Grade 3 and medically attended events during the 4-day follow-up and the 7-day follow-up period (i.e., the day of vaccination and 6 subsequent days), following each dose and overall dose and overall participant. This summary will be repeated by age group.
- The number and percentage of participants, with exact 95% CIs, reporting administration site solicited events will be summarized separately for all grades, Grade 3 and medically attended events during the 4-day follow-up and the 7-day follow-up period (i.e., the day of vaccination and 6 subsequent days), following each dose, overall dose and overall participant. This summary will be repeated by age group.
- The number and percentage of participants, with exact 95% CIs, reporting systemic solicited events will be summarized separately for all grades, Grade 3 and medically attended events during the 4-day follow-up and the 7-day follow-up period (i.e., the day of vaccination and 6 subsequent days), following each visit and overall visits and overall participant. This summary will be repeated by age group.
- Duration in days of solicited events will be summarized as follows:
  - Duration (days) of solicited administration site events will be summarized following each dose and overall,

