  - Duration (days) of solicited systemic events will be summarized following each visit and overall,
  - where duration for the above solicited events summaries is defined as:
    - Duration = (End date – Start date) + 1, for AEs with Grade > 0
      - If a solicited AE is still Grade > 0 at Day 30, the end date will be considered equal to vaccination date + 29 days.
- Number of days with Grade 3 solicited events will be summarized as follows:
  - Number of days with Grade 3 solicited administration site events will be summarized following each dose and overall,
  - Number of days with Grade 3 solicited systemic events will be summarized following each visit and overall,
  - where number of days with Grade 3 events is derived as the sum of all post-vaccine days with known Grade 3 for the events category (administration site events or systemic events), recorded up to Day 30 post-vaccine.
- For fever, the number and percentage of participants reporting fever by half degree (°C) cumulative increments in applicable systemic event summaries.
- The percentage of participants with each solicited administration site event and solicited systemic event (any grade and Grade 3) will be represented graphically for each group after each dose, during the 4-day and 7-day follow-up period.
- All solicited administration site events will be included in a listing.
- All solicited systemic events will be included in a listing.

- Sensitivity analysis will be performed to present differences in severity/intensity scales between participant and principal investigator assessments for solicited events: erythema, swelling and fever. All summaries and listings aside from this sensitivity analysis are based on the participant assessments – only the sensitivity outputs will be based on the investigator assessment. This will be summarized separately for the solicited administration site events (erythema and swelling) and for the solicited systemic event (fever). The differences between participant and principal investigator assessments will be included in a listing.
- Subgroup analysis will be created for the solicited administration site events and the solicited systemic events within 7 days of each dose split by age category, race, ethnicity and gender.

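### Protocol Table 8 fixes the RSV injection arm by group, which adds an avoidable but minor confound to the descriptive RSV-site displays, mainly for pain

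*Protocol*

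**What the plan says.** The laterality row of Protocol Table 8 (Section 6.1) reads, for the RSVPreF3 OA vaccine, "Co-ad group: Dominant Control group: Non-dominant". For HZ/su the same row gives the non-dominant arm in both groups. No reason is given for treating the two vaccines differently.

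The groups also differ in when the RSV vaccine is given. Co-Ad receives it at Visit 1 together with HZ/su dose 1. For Control, Protocol 4.1 specifies "Visit 2 (Day 31) in which participants will receive RSVPreF3 OA investigational vaccine", with no other injection at that visit.

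Solicited site events are displayed per vaccine and per dose:
- The estimand in SAP 2.4 is the percentage, with exact 95% CI, of "participants with solicited administration site events within 7 days after each vaccine administration (Days 1-7 after each vaccine, HZ/su and RSVPreF3 OA".
- SAP 16.1.1 adds that the number and percentage of participants "reporting administration site solicited events will be summarized separately for all grades, Grade 3 and medically attended events", following each dose, and that each event is "represented graphically for each group after each dose, during the 4-day and 7-day follow-up period".

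SAP 16 rules out statistical comparison of the groups on safety. Protocol 6.4 has laterality recorded in source documents. SAP 14 refers to Table 8 for dosing instructions and route. Neither document connects injection side with the reading of the RSV-site results.

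**The concern.** Safety and reactogenicity of the two vaccines, given together or separately, is a stated secondary objective, and the descriptive site-event displays are the evidence for its local part. Side-by-side percentages invite readers to compare the groups even though no test is run. For the RSV injection, that comparison sets a dominant arm against a non-dominant arm for every participant dosed according to Table 8.

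This is most plausible as a problem for pain. Grade 2 in Protocol Table 23 is defined as "Painful when limb is moved and interferes with everyday activities", and the other pain grades also refer to everyday activities. A grade that depends on using a limb could depend on which limb was injected. What is at stake is how a descriptive contrast is explained, not a formal conclusion.

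**Working it through.** There is no plan figure to reproduce, so the check is of the text and of what can be estimated.

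**1. Side by vaccine and group (Protocol Table 8, Section 4.1)**

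| Injection | Co-Ad | Control | Same side? |
|---|---|---|---|
| HZ/su dose 1 | Visit 1, non-dominant | Visit 1, non-dominant | Yes |
| RSVPreF3 OA | Visit 1, dominant | Visit 2, non-dominant | No |
| HZ/su dose 2 | Visit 3, non-dominant | Visit 3, non-dominant | Yes |

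With about 265 participants per group, RSV side is planned as 265 dominant and 0 non-dominant in Co-Ad, and 0 dominant and 265 non-dominant in Control.

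**2. Can an analysis separate side from group?** Let g = 1 for Co-Ad and 0 for Control, and d = 1 for the dominant arm. For the RSV injection d = g for everyone, so

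E(Y) = a + b·g + s·d = a + (b + s)·g.

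Only the sum b + s can be estimated. The design matrix [intercept, group, side] has rank 2 with 3 columns. Any side effect of s percentage points passes in full into the apparent Co-Ad minus Control difference. The documents give no value for s. An assumed range of 0 to 10 points would give 0 to 10 points of apparent difference.

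**3. Scale of the display (assumed event rates of 30% to 70%, n = 265 per group).** The sampling half-width of a difference is 1.96·√(2p(1−p)/265), which is 7.8 points at p = 0.3 or 0.7 and 8.5 points at p = 0.5. This shows only the precision of the contrast. It is not evidence about s.

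**4. Is the mismatch forced?** No. Opposite arms are needed only at Co-Ad Visit 1, where two vaccines are given. Control receives RSV alone at Visit 2, so either arm is free.

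**5. What would matching move?** Each participant has 3 injections (1 RSV and 2 HZ/su), so there are 3 × 265 = 795 per group. Control now has 0 of 795 in the dominant arm. With sides matched, this becomes 265 of 795 (one of three per participant) or 530 of 795 (two of three), depending on which vaccine goes in the dominant arm. These counts measure what the change would move; they do not measure bias.

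**The case against.** The strongest reply is that no harm is shown. No passage says that arm dominance changes local reactions; the idea is inferred from the wording of the pain scale. Only Grade 2 mentions limb movement, Grade 3 turns on pain at rest, and any-grade pain does not depend on those thresholds. Erythema and swelling are graded in millimetres, so the limb-use argument does not reach them. All of this stands and confines the point mainly to pain.

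Table 8 also has a logic of its own: the dominant arm is used only when two vaccines are given at one visit, and use of a second arm could be seen as part of co-administration. That is a fair reading. It explains why one Co-Ad vaccine goes in the dominant arm, but not why the RSV side must differ from Control.

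The contrast is confounded in other ways. RSV is given at a different visit, Control has already had HZ/su dose 1, and "The participant and principal investigator (PI) will not be blind to the intervention administered". This is true, but those differences follow from the sequential, open-label design, and the arm does not.

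Finally, the displays are not fully specified in what is supplied. SAP 16.1 says that, for co-administered interventions, "an administration site event recorded for a participant following multiple study interventions will be counted as only one occurrence", so some Co-Ad summaries may not be specific to the RSV site. The output templates mentioned in SAP 8 are not among the documents, so a laterality footnote cannot be ruled out. The per-vaccine estimand and the per-dose displays nevertheless remain.

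**Conclusion.** The point holds as a minor, cheaply mended weakness. If Table 8 is followed, injected arm is completely aliased with group for the RSV injection, avoidably so, and no adjustment can recover the distinction. The concern is plausible mainly for injection-site pain. It rests on the assumption that dominance might affect pain reports; size and direction are unknown, and the effect may be zero.

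A reader might infer more than the documents support:
- **That Co-Ad RSV-site pain will be overstated, or understated.** The documents give no basis for either direction.
- **That erythema and swelling are equally in doubt.** They share the aliasing, but not the limb-use argument.
- **That the trial's conclusions are weakened.** The three primary endpoints are antibody ratios, their power does not involve injection side, safety has no formal between-group test, and the holding rules in Protocol 4.5 apply to the Co-Ad group alone.
- **That matching sides would isolate the effect of co-administration.** Visit timing, prior HZ/su dose 1 and open-label reporting would still differ.

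**What to change.** **If dosing can still change:** reconcile the laterality entries in Table 8 so that each vaccine is given on the same side in both groups, keeping opposite arms at Co-Ad Visit 1. Either assignment meets this, and the choice of arm is the sponsor's. The cost is one Table 8 entry (RSV, Control) if HZ/su stays as it is, or three entries (RSV Co-Ad, HZ/su Co-Ad, HZ/su Control) for the other assignment, plus site instructions. The downside is that one or two of the three injections per Control participant move to the dominant arm.

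**If dosing is complete:** this may be so, since SAP version 3.0 is dated 23 July 2024 and the protocol April 2023, but the documents do not say. In that case keep the planned summaries and add one sentence to the RSV-site pain outputs, such as: *RSV injection side differed by group by design (dominant arm in Co-Ad, non-dominant arm in Control).* A table by actual side is not worth adding. If Table 8 was followed it would show about 265/0 against 0/265 and could not separate side from group.
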